1. OBJECTIVES

1.1. Primary Objective:

- 1.1.1. **Phase I:** To determine the DLT and MTD of the combination of azacitidine (AZA) and a tyrosine kinase inhibitor (TKI) in patients with chronic myeloid leukemia (CML).
- 1.1.2. **Phase II:** To determine the clinical activity of the combination of AZA and a TKI in patients with CML in complete cytogenetic remission (CCyR) with minimal residual disease.

1.2. Secondary Objectives:

- 1.2.1. **Phase I**
 - 1.2.1.1. To determine the clinical activity of the combination of AZA and a TKI in patients with CML
- 1.2.2. **Phase II**
 - 1.2.2.1. To determine the safety of the combination of AZA and a TKI in patients with CML in CCyR with minimal residual disease.
- 1.2.3. **Both phases**
 - 1.2.3.1. Determine the effect of therapy over DNA methylation
 - 1.2.3.2. Investigate the correlation of DNA methylation and response to therapy

2. BACKGROUND

2.1. Chronic Myeloid Leukemia

Chronic myeloid leukemia (CML) is a pluripotent stem cell disorder characterized by the presence of the Philadelphia (Ph) chromosome in the leukemic cells. The Ph chromosome results from a (9;22) translocation in which the *c-ABL* oncogene has moved from chromosome 9 into the *BCR* (breakpoint cluster region) gene on chromosome 22, resulting in a chimeric *BCR-ABL* gene¹⁻³. This is the causative abnormality in CML. The fused gene encodes an 8.5 kb chimeric mRNA^{4,5}, which is translated into a 210-kDa protein⁶. This p210 BCR-ABL protein functions as a constitutively activated tyrosine kinase and is uniquely present in the leukemic cells of CML patients⁷. The breakpoint in the *BCR* gene occurs either between *BCR* exon b2 and b3 or between *BCR* exons b3 and b4. Therefore, in the mature *BCR-ABL* mRNA, either b2 or b3 is spliced to *ABL* exon a2, which results in two alternative chimeric p210 BCR-ABL proteins, with either a B2A2 or B3A2 junction⁸.

2.2. Tyrosine Kinase Inhibitor (TKI) Therapy

Imatinib is a low molecular weight phenylaminopyrimidine designed to selectively inhibit BCR-ABL tyrosine kinase activity⁹, and is now the standard therapy for newly diagnosed patients with CML who do not undergo allogeneic stem cell transplant¹⁰.

Results of the pivotal IRIS trial have shown that over 80% of patients achieve a CCyR, with most of these responses being durable. After 7 years of follow-up, the event-free survival rate is 81% and the survival free from transformation to accelerated or blast phase is 92%.¹¹ For patients who develop resistance or intolerance to imatinib, effective therapy with second generation tyrosine kinase inhibitors has been developed. Two of these agents (dasatinib and nilotinib) are currently available, and others are under development (e.g, bosutinib). Approximately 50% of patients treated with these agents after imatinib failure achieve a CCyR, and these responses are also durable in most patients.

Several reports have shown that, among patients who achieve a CCyR with imatinib or other TKI, those who achieve a MMR (ie, at 18 months from the start of therapy) have an improved EFS and survival free from transformation to accelerated or blast phase compared to those with CCyR but no MMR (7-year EFS 95% vs 86%, respectively).¹² In this same analysis, none of the patients who had achieved a MMR transformed to accelerated or blast phase. Recently, it has been suggested that achieving a complete molecular response (CMR) further improves the long-term outcome of patients after treatment with imatinib. In one series, patients who had an MMR had a shorter relapse-free survival (median 44 months) compared to those that achieved CMR (median not reached, with a hazard ratio for relapse 11%).¹³ Similar results were reported from our institution, where patients with sustained complete molecular response have an estimate EFS at 7-years of 95%, compared to 85% for those with sustained MMR but no CMR, and 50% for those with CCyR but no MMR.¹⁴ Thus, improving the molecular response of patients who have already achieved a CCyR with TKI has become an important goal of therapy. It has been suggested that patients who achieve CMR may discontinue therapy with imatinib, an important goal for patients. However, discontinuation of imatinib among patient who achieve CMR results in relapse in over 50% of patients.¹⁵ Thus additional measures are needed to make treatment discontinuation a safer proposition.

2.3. Methylation and Hypomethylating Agents in CML

Increased methylation has been documented in CML and it plays a role in disease progression. The Pa promoter of Abl and several other key genes are hypermethylated in a significant percentage of patients. Methylation of this promoter increases with disease progression. Some studies have suggested an association of hypermethylation with worse prognosis, although this is still controversial.¹⁶⁻¹⁹ The p15 gene is also hypermethylated as CML progresses, with differential patterns of hypermethylation for myeloid and lymphoid blastic phases.¹⁶ Hypermethylation of Caderin-13 may be associated with high-risk features in CML and with a lower probability of response to IFN- α .²⁰

Hypomethylating agents have been investigated in CML showing clinical efficacy, although their use has been mostly limited to advanced stages of the disease. 5-azacitidine (AZA) was used in combination with chemotherapy (e.g., etoposide, mitoxantrone) for patients with CML in transformation, with 25% to 60% responding

(i.e., back to chronic phase –BCP-). A pilot study of AZA alone in 14 patients with CML resulted in 2 responses (MDACC internal data). Decitabine has been more extensively studied in CML. It was first used for patients with CML in transformation as a single agent at a dose of 50 to 100 mg/m² over 6 hours every 12 hours for 5 days every 4-8 weeks²¹. Twenty-eight of 51 (55%) patients treated in accelerated phase and 18 of 64 (28%) in myeloid blast phase had a hematologic responses (CHR in 12 and 6, respectively). Cytogenetic responses were achieved in 14% and 8%, respectively. Therapy was almost universally myelosuppressive with infections occurring in 34% of patients, with 4 (3%) treatment-related deaths. Subsequently, lower doses have been used based the optimized demethylating effect with this schedule. In one study, decitabine was used at lower doses until the minimal effective dose was reached. A dose of 15 mg/m² daily for 10 days (i.e., 15% to 30% of the dose previously used) was well tolerated and provided the best response in a variety of myeloid malignancies.²² This schedule has been investigated in 35 patients with CML who have failed imatinib therapy (12 chronic, 17 accelerated, 6 blastic). A hematologic response was reported in 23 (66%) patients (CHR 12, PHR 7, HI 4). Sixteen patients (46%) had a cytogenetic response (major 6, minor 10).²³ Preclinical studies have shown synergy between imatinib and decitabine.^{24 25} This combination was used in a phase II trial in patients with advanced phase CML, most of them previously treated with imatinib. Patients received decitabine 15 mg/m² intravenously daily, 5 days a week for 2 weeks, and imatinib 600 mg orally daily. A hematologic response was achieved in 50% and 30% of patients in accelerated and blast phase, respectively, with major cytogenetic responses in 33% and 20%, respectively.

We hypothesize that adding AZA to a TKI may improve the molecular response of patients with CML with CCyR but no MMR. If a significant number of patients convert to a CMR, we will explore whether TKI can be safely discontinued with minimal risk of relapse. Throughout the study we will measure the effect of therapy on DNA methylation in the peripheral blood and bone marrow, both global and gene-specific.

2.4. 5-azacitidine

Azacitidine, an analog of the pyrimidine nucleoside cytidine, has effects on cell differentiation, gene expression, and deoxyribonucleic acid (DNA) synthesis and metabolism.²⁶ Since the early 1970s, azacitidine has been investigated primarily in the US for the treatment of acute leukemia. Clinical studies have focused mainly on patients with disease refractory to conventional chemotherapy. Results of these investigations demonstrated activity of azacitidine in the treatment of AML. Clinical studies subsequently evaluated the effects of azacitidine in a variety of other malignant and hematologic disorders, including solid tumors, hemoglobinopathies (eg, thalassemia and sickle cell anemia), and MDS. In 1984, the Cancer and Leukemia Group B (CALGB) began a series of clinical studies with azacitidine in patients with MDS. These studies, in addition to other supportive data, led to the approval of Vidaza® (azacitidine) in May 2004 for the treatment of MDS.²⁶

Azacitidine inhibits the methylation of newly synthesized DNA by inhibiting DNA methyltransferase (DNMT).²⁷⁻²⁹ Increased methylation of DNA (hypermethylation) may result in the silencing of critical genes responsible for cell growth control and differentiation. Hypermethylation of CpG islands spanning the promoter regions of tumor suppressor genes is commonly associated with cancers.³⁰ It is now widely recognized that hypermethylation of DNA is frequently associated with myelodysplastic syndromes and other cancers,³¹⁻³³ such as renal,³⁴ melanoma,³⁵ breast,³⁶ colorectal,³⁷ non-small cell lung³⁸ and hematologic malignancies.³⁹ Azacitidine is believed to exert its antineoplastic effects through hypomethylation and cytotoxicity on abnormal hematopoietic cells in the bone marrow.⁴⁰⁻⁴⁴ Hypomethylation may restore normal function to genes that are critical for differentiation and proliferation.^{30,45,46} The cytotoxic effects of azacitidine cause the death of rapidly dividing cells, including cancer cells that are no longer responsive to normal growth control mechanisms.^{40,47-49}

The cytotoxicity of azacitidine is proportional to dose and exposure time.^{40,41} Although the mechanisms of cytotoxicity are complex and multifaceted, there is general agreement that incorporation of azacitidine into DNA and ribonucleic acid (RNA), and inhibition of protein synthesis, are critically important.⁵⁰ Cytotoxicity is greatest in cells that are proliferating (S phase) and metabolically active.⁴⁰ Cytotoxic effects may also be mediated through induction of the DNA damage response pathways.⁴⁹ Nonproliferating cells are relatively insensitive to azacitidine.⁴⁰

Toxicology studies have been conducted in mice, rats, dogs, and Rhesus monkeys.⁵¹ Most of the studies were performed during the 1970s and early 1980s according to existing guidelines and standards in place during that period. The preclinical studies identified the bone marrow, liver, kidneys, and lymphoid tissues (spleen, lymph nodes, and thymus) as the main target organs of toxicity for azacitidine.⁵¹ In single-dose studies, the lethal dose of azacitidine after intravenous (IV) administration in mice, rats, and dogs was approximately 250 mg/m². Repeated daily dosing appears to increase the toxicity of azacitidine.⁵¹ The genotoxicity of azacitidine is consistent with that of other nucleoside analogs that interact with nucleic acids.⁵¹ Likewise, similar to other agents with cytostatic properties, azacitidine was embryotoxic and reduced the reproductive performance in mice and rats.⁵¹

Limited azacitidine pharmacokinetic data are currently available. Based on human plasma concentrations of total radioactivity (which represents parent drug plus circulating metabolites), azacitidine is rapidly absorbed when given subcutaneously (SC), with maximum plasma concentrations found 0.5 to 2 hours after dosing.⁵¹ Azacitidine and/or its by-products are then rapidly cleared by the kidneys. The half-lives and percent radioactivity recovered in urine are similar following IV and SC routes of administration. The effects of renal or hepatic impairment, gender, age, or race on the pharmacokinetics of azacitidine have not been studied.⁵¹ A single dose (75 mg/m²) SC versus IV crossover study in 6 MDS subjects⁵² revealed an approximate bioavailability of 89% for the SC dose (range 52% to 128%) with mean half-lives of 0.69 hour and 0.36 hour after SC and IV administration, respectively. These results demonstrated that azacitidine is rapidly and nearly completely absorbed after SC

administration and that elimination is also rapid. The apparent SC clearance (167 L/h or 2791 mL/min) and systemic IV clearance (147 L/h) of azacitidine exceeded the glomerular filtration rate (approximately 125 mL/min) and total renal blood flow (1200 mL/min) in healthy subjects. This indicates that non-renal elimination (eg, metabolism, hydrolysis, and/or degradation) plays a role in the elimination of parent azacitidine. In addition, azacitidine 75 mg/m² was generally well-tolerated after single SC injection or IV infusion over 10 minutes.⁵²

A number of studies have looked at different parenteral doses and schedules of azacitidine, finding maximum tolerated doses of up to 500 mg/m² when administered weekly.⁵³

During the two decades between the start of the CALGB studies and the approval of azacitidine, a new understanding of MDS has developed, such as the World Health Organization (WHO) diagnostic criteria, the International Prognostic Scoring System (IPSS), and the International Working Group (IWG) response criteria. Silverman et al. reevaluated the combined data (N = 309) from 3 of the CALGB studies using the WHO classification system for MDS and AML and the IWG response criteria.⁵⁴ Using the IWG response criteria in MDS patients, response rates were between 40% and 70% in azacitidine treated patients. Ten to 17% of patients achieved a complete remission; partial remission was rare; and 23% to 36% of patients had a hematologic improvement. In patients with AML (N = 103), 35% to 48% had hematologic improvement or better responses. The median survival time for 27 patients assigned to azacitidine was 19.3 months compared with 12.9 months for the 25 patients assigned to observation.⁵⁴

A randomized international Phase III trial (Study AZA PH GL 2003 CL 001) for higher-risk MDS patients, classified by FAB as RAEB, RAEB-T, or CMML with 0-29% marrow blasts, with an IPSS of Intermediate -2 or High by central pathology/cytogenetic review was recently reported.⁵⁵ Patients were randomized to azacitidine (75 mg/m²/day x 7 days in 28 day cycles) or conventional care regimens (CCR), where CCR was pre-selected by the Investigator as best supportive care (transfusions, antibiotics, and G-CSF for neutropenic infection), low-dose cytarabine (20 mg/m²/day x 14 days in 28 day cycles); or standard chemotherapy (conventional induction/consolidation). Patients were stratified by FAB/IPSS and randomized 1:1 to azacitidine or CCR. This trial did not allow erythropoietin. Three-hundred fifty eight patients (70% male) were randomized at 79 centers to azacitidine (N=179) or CCR (N=179): best supportive care only (N=105, 59%), low-dose cytarabine (N=49, 27%), or standard chemotherapy (N=25, 14%). Median age was 69 years (range 38-88 years). The azacitidine and CCR groups were comparable for baseline patient characteristics. At baseline, 95% of patients were higher risk: RAEB (58%), RAEB-T/WHO AML (34%), CMML (3%), and other (5%). By IPSS, 87% were higher risk: Intermediate -2 (40%), High (47%), and 13% Indeterminate/other. Azacitidine was administered for a median of 9 cycles; low-dose cytarabine for 4 cycles. Median follow-up for the survival analysis was 21.1 months. Azacitidine demonstrated statistically superior overall survival compared to CCR, with a median overall survival of 24.4 months vs. 15

months for CCR (stratified log-rank $p=0.0001$, hazard ratio 0.58). Two-year survival approximately doubled in the azacitidine arm compared to CCR: 51% vs. 26% ($p<0.0001$). Azacitidine was well tolerated with safety data consistent with previous reports.

Further details can be found in the azacitidine Investigator's Brochure, which contains comprehensive pharmacology, toxicology, pharmacokinetics, pharmacodynamics, metabolism, preclinical, and clinical efficacy and safety data information.⁵¹

3. Criteria for Patient Eligibility

3.1. Inclusion Criteria

- 3.1.1. Patients 16 years or older with Philadelphia chromosome (Ph)- or BCR/ABL-positive CML (as determined by cytogenetics, FISH, or PCR).
- 3.1.2. Patients must have received FDA-approved TKI therapy for at least 18 months and not have increased their dose of FDA-approved TKI in the last 6 months. Patients participating on frontline protocols 2005-0048 (nilotinib) and 2005-0422 (dasatinib) are eligible for enrollment on this study.
- 3.1.3. Phase II patients must be in complete cytogenetic remission.
 - 3.1.3.1. For the phase I portion of the study, patients may be included without a complete cytogenetic remission provided they are in chronic phase
- 3.1.4. Phase II patients must have detectable BCR-ABL transcript levels meeting at least one of the following criteria:
 - 3.1.4.1. Patient has never achieved a major molecular response, and transcript levels have shown in at least two consecutive measures separated by at least 1 month to have increased by any value, or
 - 3.1.4.2. Achieved a major molecular response that has been lost with an increase in transcript levels by at least 1-log, confirmed in two consecutive analyses separated by at least 1 month, or
 - 3.1.4.3. The patient has received therapy for at least 2 years and does not have a sustained major molecular response, or
 - 3.1.4.4. The patient has received therapy for at least 5 years and does not have a sustained complete molecular response.
 - 3.1.4.5. Patients included in the phase I portion of the study are eligible regardless of their level of BCR-ABL transcripts.

- 3.1.5. Patients must not have had a known continuous interruption of imatinib therapy of greater than 14 days or for a total of 6 weeks in the 6 months prior to enrollment.
- 3.1.6. Patients must sign an informed consent indicating that they are aware of the investigational nature of this study in keeping with the policies of the hospital.
- 3.1.7. ECOG performance status ≤ 2 .
- 3.1.8. Adequate organ function defined as: bilirubin $< 2x$ upper limit of normal (ULN) (unless associated with Gilbert's syndrome), and ALT or AST $\leq 2.5x$ ULN.
- 3.1.9. ANC $\geq 1 \times 10^9/L$ and platelets $\geq 50 \times 10^9/L$.
- 3.1.10. Serum creatinine < 1.8 mg/dL or creatinine clearance greater or equal than 40 cc/min as defined by the Cockcroft-Gault Equation*. Males(mL/min): $(140 - \text{age}) * \text{ABW}(\text{kg}) / 72 * (\text{serum creatinine}(\text{mg/dl}))$; Females (mL/min): $0.85 * (140 - \text{age}) * \text{ABW}(\text{kg}) / 72 * (\text{serum creatinine}(\text{mg/dl}))$
- 3.1.11. Women of childbearing potential should be advised to avoid becoming pregnant and practice effective methods of contraception. Men should be advised not to father a child while receiving treatment with azacitidine. Azacitidine is classified as Pregnancy Category D. Females of childbearing potential: Recommendation is for 2 effective contraceptive methods during the study. Adequate forms of contraception are double-barrier methods (condoms with spermicidal jelly or foam and diaphragm with spermicidal jelly or foam), oral, depo provera, or injectable contraceptives, intrauterine devices, and tubal ligation. Male patients with female partners who are of childbearing potential: Recommendation is for male and partner to use at least 2 effective contraceptive methods, as described above, during the study.
- 3.1.12. Women of childbearing potential should have a pregnancy test within 7 days before initiation of study drug.

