3.2. Exclusion Criteria

- 3.2.1. Patients receiving any other investigational agents
- 3.2.2. Patients who are pregnant or breast-feeding
- 3.2.3. Patients with clinically significant heart disease (NYHA Class III or IV)
- 3.2.4. Known or suspected hypersensitivity to azacitidine or mannitol.
- 3.2.5. Patients with advanced malignant hepatic tumors.

4. Treatment Plan

4.1. **TKI:** Patients will continue receiving TKI at the dose they had been receiving during the last 6 months.

4.2. **AZA:**

Phase I: patients will be treated in cohorts of 3. The starting dose will be dose level 0 (50 mg/m²/d x 3 days subcutaneous or intravenous; Table 1).

4.2.1. At least 3 patients will be entered at each level. All patients treated at any one dose level must have been observed for at least four weeks before escalating to the next dose level. Patients who come off study prior to the first four weeks and have not experienced a DLT will be replaced.

Table 1: Dose escalation levels	
Dose level	AZA (mg/m ² /d x 3 days)
-3	25 (1 day only)
-2	25 (2 days only)
-1	25
0	50
1 (Target dose)	75
2	75 (for 5 days)
3	75 (for 7 days)

4.2.2. Dose escalation will be done as follows:

Dose-limiting toxicity in	Result
0/3	Escalate to next level
1/3	Enter 3 more patients
≥2/3 or ≥ 2/6	MTD exceeded. This dose level will be declared the maximally administered dose. Expand previous level to include a total of 6 patients if not already accrued to this number.

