4.5.3.2. Hematologic Toxicity

If granulocytes are $<0.5 \times 10^9/L$ or platelets are $<40 \times 10^9/L$, hold therapy until granulocytes are above $10^9/L$ and platelets are above $60 \times 10^9/L$, then resume therapy.

If recovery takes more than 2 weeks, resume TKI at 1 dose level reduction from the dose the patient was receiving at the time therapy was interrupted.

If recovery takes less than 2 weeks, resume TKI at the same dose the patient was receiving at the time treatment was interrupted. If myelosuppression recurs, resume TKI at one dose level reduction from the dose the patient was receiving at the time the treatment was interrupted.

If a similar degree of toxicity returns, a further dose reduction by one dose level can be performed, using the above procedures.

4.5.3.3. The usual dose levels for dose adjustments are as follows:

Imatinib (mg/d)	Dasatinib (mg/d)	Nilotinib (mg/d)
800	140	800
600	100	600
400	70	400
300	50	300
200	40	200
100	20	150

4.5.3.3.1. The maximum allowable daily doses of TKI are: dasatinib 140 mg/d, nilotinib 800 mg (usually as 400 mg BID), and imatinib 800 mg.

4.5.3.4. Modifications of dose schedules other than the above will be allowed within the following guidelines:

- Further dose reductions can be made to keep toxicity grade ≤ 2 .
- Dose adjustments by more than 1 dose level at a time can be considered when judged in the best interest of the patient (e.g., neutropenia with sepsis, bleeding requiring platelet transfusions) when toxicity has resolved.
- A patient who has had a dose reduction because of any reason may have their dose re-escalated provided the patient has remained free of toxicity requiring dose adjustments as defined above for at least 1 month. Escalation will be made by 1 dose-level increments only, and not more frequent than every month.

4.5.4. **AZA:** dose modifications for toxicity will be done according to the following guidelines:

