4.5.5. **Dose Escalation:** Patients that do not achieve an improvement in molecular response after 3 months (eg., from major to complete or from non-major to major) and have experienced no grade ≥ 3 toxicity may have the dose of AZA escalated by one dose level. Patients who have had a prior dose reduction of AZA and who have no toxicity for at least 1 month of therapy may increase the dose of AZA following the guidelines mentioned above. Dose escalation of the TKI is also allowed according to institutional guidelines. However, concomitant dose escalation of the two agents is not allowed. Patients who have had dose escalation of TKI cannot have dose escalation of AZA within 2 months of this escalation.

4.5.6. Occasional missed doses of TKI will not be considered a deviation. Missed doses of ≥ 2 weeks without adequate justification will be considered a protocol deviation.

4.5.7. **Duration of Therapy:** Patients may receive therapy for six cycles. After completion of the 6th cycle, patients may continue therapy if in the opinion of the investigator there is clinical benefit provided there has been no grade 3 or higher non-hematologic toxicity attributable to AZA at the doses being administered.

4.5.7.1. Patients who achieve a major or complete molecular remission can hold therapy with AZA and/or TKI and be monitored with PCR. If there is reappearance of transcripts detectable by PCR, therapy with one or both agents can be resumed at the doses being administered at the time treatment was interrupted.

4.5.8. **Concomitant Medications**

4.5.8.1. Patients may not receive any other treatment for CML while on study. This includes the use of hydroxyurea and anagrelide.

4.5.8.2. The use of other medications for management of comorbidities or adverse events is allowed as clinically indicated.

5. **Evaluation During Study**

5.1. **Pretreatment Evaluation** (within 7 days from treatment start, unless otherwise specified)

5.1.1. A complete history and physical examination including performance status.

5.1.2. CBC, platelet count and differential (differential not required if $WBC < 0.5 \times 10^9/L$), total bilirubin, SGPT (or SGOT), and creatinine within 1 week.

- 5.1.3. Bone marrow aspirate for morphology and cytogenetics or FISH (if not done within 3 months).
- 5.1.4. Pregnancy test (blood or urine) for female patients of childbearing potential within 7 days before initiation of study drug dosing.

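### Entry rules do not require a steady TKI dose before baseline, and the analysis does not say how a one-log fall is scored once the TKI has been raised on study

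*Combined protocol and SAP*

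**What the plan says.** **Entry.** Section 3.1.2 requires at least 18 months of TKI therapy and that patients "not have increased their dose of FDA-approved TKI in the last 6 months". No criterion in 3.1 or 3.2 mentions a reduction. The only other rule on TKI exposure, 3.1.5, excludes a "known continuous interruption of imatinib therapy of greater than 14 days or for a total of 6 weeks" in the 6 months before enrolment; it concerns interruptions and names imatinib only.

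**Molecular entry routes (phase II).** Section 3.1.4.1 admits a patient who has never had a major molecular response if "transcript levels have shown in at least two consecutive measures separated by at least 1 month to have increased by any value". Section 3.1.4.2 admits one who "Achieved a major molecular response that has been lost with an increase in transcript levels by at least 1-log", with confirmation. Neither sets a condition on the TKI dose while the rise was measured. Sections 3.1.4.3 and 3.1.4.4 need no rise, and 3.1.4.5 exempts phase I.

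**Baseline and starting dose.** Section 5.1.5 accepts a quantitative PCR done within the previous 3 months. Section 4.1 states: "Patients will continue receiving TKI at the dose they had been receiving during the last 6 months".

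**TKI increases on study.** Section 4.5.3.4: "A patient who has had a dose reduction because of any reason may have their dose re-escalated", after at least 1 month without toxicity that requires adjustment. Section 4.5.5: "Dose escalation of the TKI is also allowed according to institutional guidelines". Section 7.3, by contrast, lists an increase in TKI dose among the criteria for removal.

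**Analysis.** The phase II endpoint in 9.3 is a fall of at least one log, or undetectable transcripts, within 12 months. Section 9.4 counts as failures those patients who withdraw within 12 months without a molecular response. Neither section mentions TKI dose.

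**The concern.** The trial has one arm, so a one-log fall is credited to azacitidine on the premise that the background TKI did not change. Section 3.1.2 guards that premise in one direction only. A patient whose TKI was reduced, say, 2 to 4 months before entry is eligible. The baseline PCR may then fall before the reduction, or after it while transcripts are still moving. In phase II the rise that qualifies the patient under 3.1.4.1 or 3.1.4.2 may itself follow the reduction. That is an inference: the documents report no such case and give no frequency.

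Two different consequences follow. If the reduced dose continues, azacitidine may have to overcome a rising transcript level, and power is lost. If the TKI is raised again on study, part or all of a one-log fall may come from the TKI, and the plan has no rule that keeps that fall out of the response count.

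**Working it through.** **Inputs from the plan.** N = 36 (9.3). Null response rate 5%, alternative 20%, one-sided 5% test, stated power 87% (9.4).

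**Step 1: reproduce the stated power.** With X ~ Bin(36, p), find the smallest r for which P(X ≥ r | p = 0.05) is at most 0.05.
- r = 4: 0.104, too large.
- r = 5: 0.0324. Power P(X ≥ 5 | p = 0.20) = 0.873.

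The exact test at 5 or more of 36 therefore gives the stated 87%. Section 9.4 also calls the study positive if a 20% response is reached. Since 0.20 × 36 = 7.2, that means 8 or more responders: type I error 0.0003 and power 0.434. Both cutoffs are carried below.

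**Step 2: add recently reduced patients.** Let k of the 36 be recently reduced with response probability q, and let the other 36 − k respond with probability p. The total is Bin(k, q) + Bin(36 − k, p), evaluated by exact convolution. The documents give neither k nor q, so k = 2, 4, 6 and the ranges of q below are assumptions.

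**Step 3: reduced dose continued.** p = 0.20 in the others; q = 0 to 0.05. Cutoff 5 of 36.

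| k | Expected responders, k·q + (36 − k)·0.20 | Power |
|---|---|---|
| 0 | 7.2 | 87.3% |
| 2 | 6.8 to 6.9 | 83.8% to 84.7% |
| 4 | 6.4 to 6.6 | 79.6% to 81.7% |
| 6 | 6.0 to 6.3 | 74.5% to 78.3% |

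With q at or below 5%, type I error cannot exceed 3.2% here.

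**Step 4: TKI restored on study, azacitidine without effect.** p = 0.05 in the others; q = 0.25 to 0.50 from the TKI alone.

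| k | Expected responders, k·q + (36 − k)·0.05 | Type I error, ≥ 5 of 36 | Type I error, ≥ 8 of 36 |
|---|---|---|---|
| 0 | 1.8 | 3.2% | 0.03% |
| 2 | 2.2 to 2.7 | 6.3% to 11.1% | 0.1% to 0.2% |
| 4 | 2.6 to 3.6 | 10.8% to 27.0% | 0.3% to 1.2% |
| 6 | 3.0 to 4.5 | 17.0% to 48.3% | 0.6% to 4.5% |

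**Step 5: can such a fall be scored as a response?** Sections 4.5.3.4 and 4.5.5 allow the increase, while 7.3 removes the patient for it. Under 9.4, withdrawal is a failure only for a patient without a molecular response, so a fall recorded before removal stays a response. Where 4.5.3.4 or 4.5.5 is followed and the patient stays, a fall after the increase meets the 9.3 definition as written. Whether a fall first seen after removal counts is not addressed.

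**The case against.** The strongest case on the other side is that the one-directional rule is deliberate. A recent increase can create false responses; a reduction that is simply continued works against response and cannot inflate type I error. Section 7.3 names a TKI increase as a reason for removal, and restoring the dose shortly before entry would breach 3.1.2. Section 4.5.3.4 sits among the on-study toxicity rules and was probably written for reductions made on study. Section 4.1 speaks of continuing, which ordinarily means the current dose. The transcript-rise routes matter for fewer patients than they might seem to: a patient without a sustained major response after 2 years qualifies under 3.1.4.3 with no rise at all.

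Most of this stands. It limits the entry gap itself to a modest loss of power and a baseline of uncertain meaning. It does not settle the scoring question, because 7.3 is contradicted by 4.5.3.4 and 4.5.5, and removal does not turn a recorded fall into a failure.

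A reader might infer two stronger things. One is that the entry gap by itself inflates the false-positive rate; step 3 shows that it does not, since the TKI must also be raised on study. The other is that 4.1 sends recently reduced patients back to their earlier, higher dose without this being an increase. The wording does not exclude that reading, but nothing in the documents supports it over the ordinary one.

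**Conclusion.** The point holds in a limited form. Section 3.1.2 does not secure the dose stability that 4.1 presumes, so a recently reduced patient can enter without a steady-dose baseline. With the reduced dose continued, the loss is about 3 points of power for 2 such patients and 9 to 13 points for 6, if they respond at 0-5%.

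Bias towards a positive result requires a TKI increase on study. At 5 or more of 36 the illustrated type I error is 6% to 48%; the upper figure needs 6 patients, all restored, each with a 50% chance of a one-log fall. At 8 or more of 36 it stays at or below 4.5%, although power at that cutoff is only 43% before any loss. The number of such patients and their chance of a fall are assumptions, so the ranges show sensitivity and are not forecasts.

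The part that most needs action is the missing scoring rule, because the plan both permits and forbids a TKI increase. It affects any patient whose TKI is raised, not only those recently reduced. The stated 87% power is correct for the 5-of-36 test and is not in dispute.

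**What to change.** 1. **Scoring rule, 9.3-9.4 (main change).** Define the TKI dose on the day of the baseline PCR as the reference dose. In the primary analysis, count a one-log fall first seen after the TKI dose exceeds that reference as non-response. A fall documented before any such increase would still count. State that the rule applies whether or not the patient has been removed under 7.3.
2. **Entry wording, 3.1.2 and 4.1 (secondary).** Reconcile the two on dose stability before entry, for example by making the 6-month rule cover any dose change.
3. **On-study increases.** Reconcile 4.5.3.4 and 4.5.5 with 7.3. Which clinical rule should prevail is for the sponsor and investigator; no dose is proposed here.

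The cost is a short amendment with no change to the planned 36 patients. A few genuine responses may be counted conservatively, and if the entry rule is widened, a few recently reduced patients will enter later. The TKI dose must be recorded on the day of the baseline PCR and at each later change.
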